#### **Clinical Procedure:**

#### **Diagnosis and Treatment Plan**

- 1. Subjects will be informed in detail about the sequencing of the events that would take place during the study. This will include risks, benefits and alternatives for treatment.
- Preliminary impressions will be made with polyvinyl siloxane impression material (Exafast, GC America Inc., Alsip, IL). Diagnostic casts will be fabricated in type III dental stone (Microstone, Whip Mix, Louisville, KY).
- 3. The diagnostic casts will be articulated with the use of a face-bow on a Panadent semiadjustable articulator (Panadent Corporation, Colton, CA) using interocclusal record made with polyvinyl siloxane (Exabite, GC America Inc., Alsip, IL) and wax record bases.
- 4. The diagnostic waxing of the missing teeth will be fabricated with tooth-colored wax (Pro-Art, Ivoclar Vivadent, Inc., Williams, Amherst, NY), and then will be duplicated in type III dental stone for partially edentulous patients. In case of completely edentulous patients, denture teeth will be set up in an optimal position on a base plate based

on the conventional complete denture fabrication. A silicone lab putty (Polysiloxane Coltene Lab-Putty, Coltene Whaledent Inc. Cuyahoga Falls, OH) impression will be taken of this denture setup.

- 5. A vacuum-formed radiographic template (Polypropylene Coping Sheet, Ultradent Products, South Jordan, UT) with auto-polymerizing acrylic resin (Jet, radiopaque teeth color, Lang Dental, Wheeling, IL) will be fabricated from the duplicated cast for partially edentulous patients. For completely edentulous patients, a radiographic template will be fabricated from the silicone putty impression with radiopaque color auto-polymerizing acrylic resin for teeth and clear color for the base (Jet, radiopaque teeth color, Lang Dental, Wheeling, IL). These templates will be used in conjunction with the cast for identifying the desired locations of the dental implants.
- 6. All patients will undergo radiographic evaluations before sinus augmentation. A conebeam computed tomography (CBCT) scan (NEWTOM full volume scan of the maxilla) would be taken with the radiographic template. (The radiographic evaluation prior to sinus augmentation is standard protocol)

#### **Pre-operative procedure**

- At a pre-surgical appointment, the patient's vital signs (blood pressure, pulse rate) will be recorded and the patient's medical history will be updated. At this point, patients will be randomly assigned to Group A or B.
- 2. Patients will be given the following three choices of anesthesia for the sinus surgery:
  - a) Local anesthesia (LA) only.
  - b) LA in conjunction with oral sedation (Halcion 0.25mg, Roxane Laboratories Inc., Columbus, OH). Administered 30 minutes before the appointment.

c) LA in conjunction with intravenous (IV) sedation.

A patient who chooses IV sedation will have a pre-surgical interview with the anesthesiologist (Surgery Center for Dentistry, Loma Linda University School of Dentistry) who will conduct sedation at the time of the surgery.

- 3. All patients will be questioned regarding drug allergy and prescribed with appropriate antibiotics (Amoxicillin 500 mg or Clindamycin 300mg, TID for 10 days, to start day 1 before the day of surgery) analgesic (Ibuprofen 800 mg) to take 1 tab 1 hour before the surgery and for post-operative usage as needed for pain. The patient will also be instructed to rinse with 0.12% chlorhexidine gluconate solution (Peridex, Zila Pharmaceuticals Inc., Phoenix, AZ) twice a day starting 1 week before the surgery to continue for 2 weeks after the surgery.
- 4. The radiographic template will be converted into a surgical template. The proposed implant locations in the radiographic template will be finalized and modified if necessary after reviewing the CBCT scan with the template in place. The location of the anterior wall of the sinus cavity will be marked on the surgical template.
- 5. All pre-operative and postoperative instructions will be given to the patient in an oral and written format. All of the patient's questions about the instructions will be answered.

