#### **Informed Consent:**

In accordance with the standards of conduct established by the Institutional Review Board of Loma Linda University, participants will be required to sign an informed consent. The purpose and the nature of the study will be explained to the subjects by one investigator (SU) and patient who will meet our inclusion criteria will then be invited to participate. Subjects will be required to read, understand, and sign the consent form before being enrolled in the study. Hard copy will be retained following the standard protocol set by the Institutional Review Board of Loma Linda University. Randomization – Quickcalcs software from Graphpad (Graphpad software Inc, La Jolla, CA USA) will be used to randomly assign patients. All patients will undergo sinus augmentation and will be randomly placed into two groups according to the graft material to be used in the surgical procedure. If a patient requires bilateral sinus augmentation, (two sinus on either side in the same patient) each sinus will be considered as one unit for the randomization procedure.

Group A: 10 Maxillary sinus augmentation using ABBM (InterOss).

Group B: 10 Maxillary sinus augmentation using ABBM (Bio-Oss).

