#### **Surgical procedures**

 On the day of surgery, the patient will be asked to rinse their mouth with 0.12% chlorhexidine gluconate solution (Peridex) for 3 minutes prior to the surgery. After being seated, the patient will be monitored for blood pressure, pulse rate, and oxygen level and circumoral area will be scrubbed with a Povidone-Iodine swab stick (Aplicare, Aplicare Inc., Branford, CT) and the patient will be draped. Oxygen will be provided to the patient through the nasal cannula at a minimum rate of 3 liters/minute, if the patient chooses to be sedated.

- 2. All the patients will be treated with the same surgical technique consisting of sinus floor augmentation via a lateral approach. All surgeries will be performed by one surgeon (SU). After appropriate local anesthetic administration (2% Xylocaine with epinephrine 1:100,000, Dentsply International Inc., York, PA) administration, a midcrestal incision will be made and a vertical releasing incision will be made anteriorly at the appropriate location. A full-thickness flap will be reflected to expose the lateral wall of the sinus.
- 3. Each antrostomy will be outlined with a round carbide bur (KOMET USA, Rock Hill, SC) ensuring that the inferior border will be at least 2 mm superior to the sinus floor. If the lateral bone window is not completely separated from the surrounding bone, a mallet and chisel (H & H Company, Ontario, CA) will be used to facilitate complete separation.
- 4. Sinus membrane will be carefully elevated to create space for the bone graft. The bony remnant from the window will be elevated with the sinus membrane to form the roof of the future space for the bone graft material. The membrane's integrity will be checked visually and with the Valsalva test. If a perforation to the sinus membrane occurs, the surgeon will evaluate the site prior to proceeding. If the perforation is < 5 mm in diameter and is able to be repaired, the perforation will be isolated and a resorbable collagen membrane (Bio-Gide, Geistlich, Wolhusen, Switzerland) will be placed over the area, in such a position so as to overlay unaffected membrane by at least 3 mm in all directions. Then, the surgeon will continue with the procedure as

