planned. Any perforation > 5 mm will be excluded from this study. Prior to the placement of the graft, the mesial and distal margins of the lateral window will be marked on the surgical template. A line connecting these two marks will be made following the outline of the inferior margin. The inferior and superior margins will be measured from this line and these measurements will be recorded.

- ABBM (InterOss large particle 1-2mm) or ABBM (Bio-Oss® large particle 1-2mm) will be placed into the each sinus compartment for the two groups. Approximately 2-3 grams of graft material will be placed in each sinus compartment as per the individual case requirements.
- 6. Primary closure of the flap will be performed using a 5-O expanded poly tetrafluoroethylene (Gore-Tex, W.L. Gore and Associates, Inc. Newark, DE) suture material for the crestal incision and polyglactin 910 suture material (Vicryl 6-0, Ethicon, Somerville, NJ) for the vertical incision.

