#### Patient Withdrawal and/or Replacement:

If a subject decides to withdraw from the study prior to sinus augmentation, this individual will be replaced with another subject. If a perforation of the sinus membrane (> 5 mm) occurs during the surgical procedure, the site will be closed and the augmentation procedure will be aborted. This individual will be replaced with another subject.

If a subject is withdrawn from the study following sinus augmentation, all data associated with this individual will be reported but not included in the final results and analysis. If the subject is unable to attend the required post-operative sessions or is uncooperative, this individual may be dismissed from the study.

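### Graft material is assigned at a pre-surgical visit, before the membrane check that settles eligibility, and pre-graft losses are replaced: an avoidable risk of bias

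*Combined protocol and SAP*

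**What the plan says.** In order of events, the combined protocol and SAP provides as follows.

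- **Method and unit (Informed Consent, randomization text).** Graphpad QuickCalcs "will be used to randomly assign patients", with 10 augmentations in each group. In a bilateral case, "each sinus will be considered as one unit for the randomization procedure". No list-holder, envelope or other concealment is described.
- **Timing (Pre-operative procedure, item 1).** At the pre-surgical appointment: "At this point, patients will be randomly assigned to Group A or B". Item 3 of that section has patients start a mouth rinse one week before surgery, which suggests the visit is about a week or more ahead.
- **Membrane check (Surgical procedures, item 4).** One surgeon performs every operation and evaluates any perforation. The procedure continues "If the perforation is < 5 mm in diameter and is able to be repaired". Then: "Any perforation > 5 mm will be excluded from this study". Graft material first enters at the next step.
- **Replacement (Patient Withdrawal and/or Replacement).** For a perforation above 5 mm, "the site will be closed and the augmentation procedure will be aborted. This individual will be replaced with another subject". Separately: "If a subject decides to withdraw from the study prior to sinus augmentation, this individual will be replaced with another subject".
- **Blinding (Histology / MicroCT assessment).** Stated for the specimen examiners only.

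**The concern.** The null hypothesis compares two materials, and the test relies on the groups being formed by chance. Here the groups are formed at one visit and can be changed afterwards in two ways: a perforation exclusion decided in the operating room, or a withdrawal between the visit and surgery. In both cases someone may know the arm when the loss occurs. The plan does not say the surgeon is kept unaware of the assignment, and the same investigator both explains the study to patients and operates.

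Replacement adds a second exposure. The plan does not say where a replacement's assignment comes from. If it fills the vacated place in groups fixed at 10 and 10, its arm is foreseeable before that patient is approached.

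With 10 sinuses per arm, each substitution is 10% of an arm. None of this exposure is needed, because the material plays no part until the membrane check is complete.

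**Working it through.** **1. The sequence.** Set side by side, the sections give: allocation at the pre-surgical visit; possible withdrawal, with replacement; surgery and membrane elevation; membrane check and surgeon's evaluation; exclusion and replacement if above 5 mm; graft placement. Both routes to replacement can operate after allocation and before grafting. Withdrawals before the pre-surgical visit do no harm, since nobody has yet been allocated, but the withdrawal rule does not separate the two.

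**2. How often it could happen.** The plan has no figure to reproduce: it gives no perforation rate, no withdrawal rate and no basis for the sample size. Let *p* be an assumed proportion of allocated units lost before grafting, and take 20 grafted units as the target.

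- Expected allocations = 20/(1 − p)
- Expected replacements = 20p/(1 − p)
- Chance of at least one loss among the first 20 = 1 − (1 − p)^20

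| Assumed p | Expected allocations | Expected replacements | At least one loss in first 20 |
|---|---|---|---|
| 5% | 20/0.95 = 21.1 | 1.05 | 1 − 0.95^20 = 64% |
| 10% | 20/0.90 = 22.2 | 2.22 | 1 − 0.90^20 = 88% |
| 20% | 20/0.80 = 25.0 | 5.00 | 1 − 0.80^20 = 99% |

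Even at 5%, at least one replacement is more likely than not.

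**3. How much it could matter.** Suppose the worst-prognosis fraction *f* of one arm only is excluded and replaced, and prognosis as judged at the exclusion call has correlation *ρ* with the outcome. For a normally distributed outcome, with φ the normal density and z_f its f-quantile:

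bias in SD units = ρ × φ(z_f)/(1 − f)

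- f = 10%: φ(−1.282)/0.9 = 0.1755/0.9 = 0.195. With ρ = 0.3 this is 0.06 SD; with ρ = 1, 0.20 SD.
- f = 20%: φ(−0.842)/0.8 = 0.2800/0.8 = 0.350. With ρ = 0.3 this is 0.10 SD; with ρ = 1, 0.35 SD.
- ρ = 0: no bias at any f.

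A simulation of the same model (20,000 runs, 10 per arm, two-sided t test at 5%, no true difference) agreed with these biases. Type I error was 5.2% to 6.8% at f = 10% and 5.5% to 12.3% at f = 20% for ρ from 0.3 to 1. It stayed near 5% at ρ = 0.

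**4. After moving allocation.** If allocation follows the membrane check, losses after allocation by these two routes are zero, and the 20 allocated units are the 20 grafted units.

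**The case against.** The strongest reply is that the check precedes grafting, so the material cannot cause a perforation. Bias requires that knowledge of the arm alters membrane elevation, measurement, the repair decision or a patient's choice to withdraw, and also that the lost sinuses differ in prognosis. That is correct. The trial is a small pilot and the histology examiners are blinded. What stands is that the plan contains no safeguard against that chain, and that it still tests a hypothesis at P < .05.

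Four stronger readings are tempting, and the documents do not support them.

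- *The surgeon excludes smaller perforations at discretion.* The only stated trigger for exclusion, and for aborting and replacing, is a perforation above 5 mm, which is a measured threshold. The text is silent on perforations below 5 mm that cannot be repaired and on those of exactly 5 mm. That is a gap in the rules, not a stated exclusion. The Adherence to Protocol section also bars departures other than for medical conditions needing management that the protocol does not specify.
- *Replacements have a known arm.* The plan says only that another subject replaces the lost one. A fresh random assignment is equally consistent with the text, so foreseeability is conditional.
- *The surgeon knows the allocation.* This is a fair inference from silence, but the text names nobody as making the assignment or holding the list.
- *The bias has a known ceiling, or a size in percentage points.* The result depends wholly on the assumed fraction and correlation. At f = 30% and ρ = 1 it is 0.3477/0.7 = 0.50 SD. No outcome SD is given, so conversion to percentage points has no basis in the documents.

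**Conclusion.** The point holds as an avoidable risk of bias, not as a demonstrated one. The text firmly supports the sequence: allocation before the last eligibility step, then exclusion and replacement. That the surgeon could know the arm, and that a replacement's arm could be foreseen, follow from what the plan leaves unstated.

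The size runs from zero, if exclusion is unrelated to arm and prognosis, to about 0.06 to 0.35 SD if the worst-prognosis 10% to 20% of one arm only were replaced (ρ from 0.3 to 1). All rates and correlations are assumptions, and one-arm selection is a deliberately unfavourable case. It would go too far to say that the randomised comparison is already compromised. The change is worth making because the stated timing creates the exposure and moving it costs little.

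**What to change.** 1. Move the allocation step from Pre-operative procedure, item 1, to Surgical procedures, immediately before graft placement.
2. Have someone who does not operate prepare concealed, sequentially numbered assignments from the QuickCalcs list. Open one only after the surgeon has declared that sinus eligible, and record that declaration first.
3. A sinus that fails the check, or a patient who withdraws earlier, is then never allocated, and the next eligible sinus takes the next assignment. Amend Patient Withdrawal and/or Replacement so that no allocated subject is replaced for these two reasons. Report perforations over all sinuses opened.
4. Apply this per sinus in bilateral cases. Reconcile the replacement of the individual with the sinus as the unit of randomization, and say what happens to the other sinus when one fails.
5. Reconcile Surgical procedures with Patient Withdrawal and/or Replacement on perforations of exactly 5 mm and on smaller ones that cannot be repaired. The clinical handling is for the sponsor to state; nothing here asks for it to change.

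If the present timing must stay, state how a replacement is allocated and report all allocated units, exclusions and replacements by group.

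The cost is a protocol amendment, a set of envelopes or equivalent, and both materials in the operating room. Patients would not learn their material before surgery. No extra patients, visits or procedures are needed. One weakness remains: the surgeon sees each material used, so the last assignments in a fixed 10/10 list can still be guessed by counting.

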#### **Surgical procedures**

 On the day of surgery, the patient will be asked to rinse their mouth with 0.12% chlorhexidine gluconate solution (Peridex) for 3 minutes prior to the surgery. After being seated, the patient will be monitored for blood pressure, pulse rate, and oxygen level and circumoral area will be scrubbed with a Povidone-Iodine swab stick (Aplicare, Aplicare Inc., Branford, CT) and the patient will be draped. Oxygen will be provided to the patient through the nasal cannula at a minimum rate of 3 liters/minute, if the patient chooses to be sedated.

- 2. All the patients will be treated with the same surgical technique consisting of sinus floor augmentation via a lateral approach. All surgeries will be performed by one surgeon (SU). After appropriate local anesthetic administration (2% Xylocaine with epinephrine 1:100,000, Dentsply International Inc., York, PA) administration, a midcrestal incision will be made and a vertical releasing incision will be made anteriorly at the appropriate location. A full-thickness flap will be reflected to expose the lateral wall of the sinus.
- 3. Each antrostomy will be outlined with a round carbide bur (KOMET USA, Rock Hill, SC) ensuring that the inferior border will be at least 2 mm superior to the sinus floor. If the lateral bone window is not completely separated from the surrounding bone, a mallet and chisel (H & H Company, Ontario, CA) will be used to facilitate complete separation.
- 4. Sinus membrane will be carefully elevated to create space for the bone graft. The bony remnant from the window will be elevated with the sinus membrane to form the roof of the future space for the bone graft material. The membrane's integrity will be checked visually and with the Valsalva test. If a perforation to the sinus membrane occurs, the surgeon will evaluate the site prior to proceeding. If the perforation is < 5 mm in diameter and is able to be repaired, the perforation will be isolated and a resorbable collagen membrane (Bio-Gide, Geistlich, Wolhusen, Switzerland) will be placed over the area, in such a position so as to overlay unaffected membrane by at least 3 mm in all directions. Then, the surgeon will continue with the procedure as

planned. Any perforation > 5 mm will be excluded from this study. Prior to the placement of the graft, the mesial and distal margins of the lateral window will be marked on the surgical template. A line connecting these two marks will be made following the outline of the inferior margin. The inferior and superior margins will be measured from this line and these measurements will be recorded.

- ABBM (InterOss large particle 1-2mm) or ABBM (Bio-Oss® large particle 1-2mm) will be placed into the each sinus compartment for the two groups. Approximately 2-3 grams of graft material will be placed in each sinus compartment as per the individual case requirements.
- 6. Primary closure of the flap will be performed using a 5-O expanded poly tetrafluoroethylene (Gore-Tex, W.L. Gore and Associates, Inc. Newark, DE) suture material for the crestal incision and polyglactin 910 suture material (Vicryl 6-0, Ethicon, Somerville, NJ) for the vertical incision.

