#### **Post-operative instructions**

All patients will be instructed to maintain a liquid diet for 2 weeks after the sinus surgery, continue on a soft diet for one month and general diet for the remaining duration of the healing phase. If a patient presents with a removable prosthesis, the prosthesis will be evaluated for proper tissue adaptation. If the tissue adaptation is poor, the prosthesis will be relined using a soft reline material (GC Reline Soft, GC, Alsip, IL) following the surgery. The patient will be advised to avoid nose blowing and placing any undue pressure on the surgical site. The patient will be instructed to rinse gently with 0.12% chlorhexidine gluconate solution (Peridex) for the first two weeks following the surgery. Recall examinations will be scheduled two weeks following the surgery for suture removal and at 1, 3, and 6 months after sinus augmentation and 2 weeks before biopsy and implant placement. The biopsy and implant placement procedure will be performed 8 months after the grafting procedure. A CBCT scan will be taken 2 weeks before implant placement to determine the final implant position and size. (The post operative CBCT scan after sinus augmentation and prior to implant placement is standard protocol )

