#### Surgical and post-operative complications

Surgical and post-operative complications such as perforation of the sinus membrane, acute or chronic sinus infection (pain, suppuration, swelling, nasal fluid leakage), bleeding, wound dehiscence, and exposure of the graft will be recorded.

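### Patients with a membrane tear over 5 mm are excluded from the study and replaced, and nothing in the plan ensures that these tears are counted among the complications

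*Combined protocol and SAP*

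**What the plan says.** All sections are in the combined protocol and SAP.

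- **Pre-operative procedure.** Allocation is made at the pre-surgical appointment: "At this point, patients will be randomly assigned to Group A or B".
- **Surgical procedures, item 4.** Small tears stay in: "If the perforation is < 5 mm in diameter and is able to be repaired, the perforation will be isolated", covered with a membrane, and the operation continues. Large tears do not: "Any perforation > 5 mm will be excluded from this study".
- **Patient Withdrawal and/or Replacement.** For a tear over 5 mm, "the site will be closed and the augmentation procedure will be aborted. This individual will be replaced with another subject". The same section has a data rule for lost patients (reported, but kept out of the final analysis). It is worded only for withdrawal after augmentation has taken place.
- **Surgical and post-operative complications.** The list of events to be recorded opens with perforation: "Surgical and post-operative complications such as perforation of the sinus membrane, acute or chronic sinus infection". It gives no size limit, population or denominator.
- **Post-operative instructions.** The first recall, for suture removal, is timed two weeks from the surgery. The later ones are set "at 1, 3, and 6 months after sinus augmentation and 2 weeks before biopsy and implant placement".

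**The concern.** A patient whose membrane tears by more than 5 mm has already been randomized and has had a flap raised and a bony window cut under the protocol. The tear is the most severe form of the first complication on the plan's own list. The patient also remains open to other events on that list, such as sinus infection, bleeding and wound dehiscence.

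The exclusion is from the study, not from one analysis, and a replacement fills the place. The one rule that would keep a lost patient's data in the report does not reach an operation aborted before grafting. An analyst following these sections could reasonably summarize complications over the grafted sinuses only. The complication record would then look better than the surgical experience was, and a reader could not tell how many sinuses were opened to obtain those that were grafted.

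**Working it through.** The plan states no perforation rate and no complication denominator, so there is no figure of its own to reproduce. The check compares the sections and then illustrates the size under assumptions.

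**Step 1: the path of a patient with a tear over 5 mm**

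1. Randomized: yes, at the pre-surgical appointment, so an assigned group exists.
2. Operated on: yes. The membrane is checked after it has been elevated and before graft is placed.
3. In the study afterwards: no; excluded and replaced.
4. Event recorded: the complications section would include it, since it sets no size limit. The exclusion, read plainly, would remove it. No sentence says which prevails.
5. Data reported: the only reporting rule for lost patients begins after augmentation, so it does not apply.
6. Recall: the two-week visit runs from the surgery and can be read to cover the patient. The 1-, 3- and 6-month visits run from sinus augmentation, which did not happen. The last visit runs from biopsy and implant placement, which an aborted case does not reach on the study schedule.

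**Step 2: effect on a reported rate**

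Inputs from the plan: 20 patients, with 10 augmentations in each of two groups. Assumptions: one sinus per patient, recruitment continues until 20 sinuses are grafted, and k sinuses are aborted for a tear over 5 mm.

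- Counting retained sinuses only: 0/20 = 0% for every k.
- Counting every sinus opened: k/(20 + k).

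| k (assumed) | Retained only | All opened |
|---|---|---|
| 1 | 0/20 | 1/21 = 4.8% |
| 2 | 0/20 | 2/22 = 9.1% |
| 3 | 0/20 | 3/23 = 13.0% |
| 5 | 0/20 | 5/25 = 20.0% |

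**Step 3: is a large tear likely to occur at all?**

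Let p be the assumed chance of a tear over 5 mm per sinus. The chance of at least one in the first 20 sinuses is 1 − (1 − p)^20. The expected number aborted on the way to 20 grafted sinuses is 20/(1 − p) − 20.

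| p (assumed) | At least one in first 20 | Expected aborted |
|---|---|---|
| 2% | 1 − 0.98^20 = 33% | 20.41 − 20 = 0.41 |
| 5% | 1 − 0.95^20 = 64% | 21.05 − 20 = 1.05 |
| 10% | 1 − 0.90^20 = 88% | 22.22 − 20 = 2.22 |
| 20% | 1 − 0.80^20 = 99% | 25.00 − 20 = 5.00 |

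At a rate of a few per cent or more, the question of how to count such a case is a practical one.

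**The case against.** The strongest reply is that the plan nowhere says large tears go unrecorded. The complications section covers perforation of any size and is not restricted to grafted or retained patients, so excluding a patient need not mean omitting the event. Complications are also not the purpose of this pilot, whose objective and null hypothesis concern new bone formation. A sinus that was never grafted has no graft core to analyse, and the tear occurs before graft is placed, so it cannot be an effect of the material.

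Much of this stands, and it rules out three stronger readings that a reader might infer:

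- **That the plan makes it impossible to show a large tear.** The documents do not support this. The recording rule could include such tears; what is missing is a statement that it does. No complication table and no denominator of 20 are described; the only outputs said to be tabulated are the histomorphometric measurements. The 0/20 figure therefore depends on retained sinuses being the ones counted.
- **That these patients have no scheduled recall, or leave follow-up on the day of surgery.** The suture-removal visit is timed from the surgery, and the post-operative section opens by addressing all patients. Only the later visits are tied to augmentation, biopsy or implant placement.
- **That the comparison of the two grafts is biased by this rule.** The order of events, tear before graft, speaks against it.

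What the reply does not remove is the conflict itself. The exclusion is worded for the whole study, and the reporting rule for lost patients stops short of aborted operations. Silence on the denominator leaves the more favourable count open.

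**Conclusion.** The concern holds as a defect in complication reporting. Two sections exclude and replace a randomized, operated patient for the most severe grade of a listed complication, and no section says that the event, or later events in that patient, will be reported. If only retained sinuses are counted, tears over 5 mm read as zero at any true frequency; with two such tears the figure should be 2/22 (9.1%).

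That size is illustrative. It rests on assumed counts, one sinus per patient and a report limited to the 20 grafted sinuses; the documents give no perforation rate, so no actual understatement can be estimated. The histologic comparison is untouched. On recall, the finding is limited to an unanswered question about the visits after two weeks.

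**What to change.** - In Surgical procedures and in Patient Withdrawal and/or Replacement, limit the exclusion for tears over 5 mm to the histomorphometric analysis. Replacement to reach 20 grafted sinuses can stay.
- In Surgical and post-operative complications, define the reporting population as every sinus in which surgery was begun, by assigned group. Report perforations by size class over that denominator and list aborted and replaced cases. The classes should be exhaustive: a tear of exactly 5 mm, or a smaller one that cannot be repaired, now falls under neither of the stated rules.
- Reconcile these three sections with Post-operative instructions on which recall visits apply to an aborted case. The schedule is for the investigators to decide.

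The cost is a few sentences and a few extra records for each aborted case. The small downside is that the reported complication rate may look less favourable. The operation, the grafts, the 5 mm threshold and the target number of sinuses do not change.
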